#### 10.4.7.2 EFFICACY REVIEW

After 100 patients have reached their 7-day visit, an efficacy review is planned to reassess the required sample size. This will be done using the methods described by Cui, Hung & Wang (1999). The sample size re-estimation (SSR) will be based on the observed conditional power at the time of the interim analysis. The re-estimated sample size will be required to be between 150 and 300 patients. Full details for the methodology of the SSR will be provided in an Interim Statistical Analysis Plan.

#### 10.4.8 ADDITIONAL SUB-GROUP ANALYSES

A number of exploratory subgroup analyses is planned, for which the study is not powered, including:

- The number of bleeding events in patients who resumed their NOAC treatment within 24 hours after extraction compared to later than 24 hours after extraction, stratified per treatment group.
- Risk factor analysis for bleeding, eg. patient demographics and procedural characteristics

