# 2 INTRODUCTION: BACKGROUND INFORMATION AND SCIENTIFIC RATIONALE

#### 2.1 BACKGROUND INFORMATION

Since the introduction of new oral anticoagulant drugs (NOACs), the number of patients treated with this class of antithrombotics is steadily increasing. For major surgical procedures, vitamin K antagonists (VKAs) are discontinued prior to the procedure and resumed thereafter. Temporary interruption of VKA treatment confers both an ischemic as well as bleeding risk. This is caused by complex pharmacokinetics during interruption, the long half-life of VKA, and concomitant bridging therapy with low molecular weight heparins (LMWH). Since there is no increased risk of major bleeding when performing minor procedures such as dental extractions on stable VKA treatment, it is current practice not to discontinue VKAs for dental extractions (1).

In contrast to VKA, little evidence is available for the periprocedural management of NOACs in dental extractions (2). The current guidelines of the European Heart Rhythm Association advise to perform dental extractions at trough level (3-6). However, in clinical practice it can be complicated to schedule the extraction at the time of the day corresponding to trough plasma levels.

We have therefore recently shown that a standardized pragmatic approach in patients who undergo dental extractions, by skipping only the dose on the morning of the extraction, regardless of timing of extraction, drug regimen or renal function, is feasible and safe (7). In a total of 52 patients, there was no difference in the procedural bleeding score or in early bleeding between NOAC patients and controls (patients without any antithrombotics). However, delayed bleeding between day 1 and day 7 occurred more frequently in anticoagulated compared to non-anticoagulated patients (7 versus none, p=0.01). Similarly, an increase in bleeding during the first postoperative week was reported in a retrospective study in patients undergoing dental extraction under uninterrupted NOAC treatment (8). The combination of peak plasma levels of the NOAC with an immature coagulum at the extraction site could trigger bleeding.

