Since bleeding events can lead to unscheduled interruption of NOAC treatment and subsequent increased risk of thrombo-embolic events, an optimal strategy to minimize bleeding events after dental extractions is required. In this interventional phase IV study, we want to assess whether adding tranexamic acid (TXA) mouthwash reduces the number of bleeding events in patients treated with NOACs undergoing a dental extraction.

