#### Exploratory analyses:

- To investigate the potential relationship between time of last NOAC dose administered prior to the extraction (regardless of specific NOAC type), time of resuming NOAC after the procedure, and bleeding events
- To investigate the potential benefit of TXA in subgroups of patients (molar versus non-molar extraction)

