#### 4.2 STUDY OUTCOMES

The procedural bleeding score is a visual analogue score (VAS) ranging from 0 (no bleeding) to 10 (unstoppable bleeding).

A reintervention is defined as any procedure in the oral cavity for the treatment of bleeding, performed by any dentist or maxillofacial surgeon, except for rinsing the extraction socket with saline.

All suspected bleeding events and reinterventions will be adjudicated by a blinded adjudicator, unaware of the assigned treatment.

Bleedings are defined as previously published (7):

- Minor bleeding: any oral bleeding experienced by the patient that does not require medical contact.
   Eg. blood on the pillow, bleeding requiring the use of additional gauzes, clear red bleeding when spitting out the mouthwash
- Clinically relevant non-major bleeding: any oral non-major bleeding requiring unplanned medical contact (by phone or with any health care professional (dentist, general practitioner, maxillofacial surgeon), with or without re-intervention
- Major bleeding: any oral bleeding requiring blood transfusion, hospitalization or resulting in death
- Early bleeding: any oral bleeding occurring after the extraction up to and including day 1 after the extraction
- Delayed bleeding: any oral bleeding occurring between day 2 and day 7

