#### 4.2.3 EXPLORATORY OUTCOMES

The following subgroup analyses are planned:

- Risk factor analysis for bleeding, eg. patient demographics and procedural characteristics
- The number of bleeding events in patients in relation to the time since stopping and resuming NOAC in relation to the dental extraction, e.g. in patients who stopped/resumed NOAC treatment within 24 hours prior/after extraction compared to more than 24 hours prior/after extraction.

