#### 7.8 RESCUE MEDICATIONS, TREATMENTS, AND PROCEDURES

The treatment of a bleeding event is considered standard-of-care and may include (at the discretion of the treating physician):

- Rinsing the extraction socket, applying hemostatic measures, removal of the false coagulum, stitching
- Interruption of the NOAC when necessary

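### The exploratory 24-hour NOAC-restart comparison ignores whether a bleed came before restart, so a bleed that delays restart counts against late restart

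*Combined protocol and SAP*

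**What the plan says.** Section 10.4.8 lists an exploratory, unpowered comparison of bleeding counts between two groups: "patients who resumed their NOAC treatment within 24 hours after extraction compared to later than 24 hours after extraction". The arms serve as strata. Section 4.2.3 gives the same idea for stopping and resuming, for example "in patients who stopped/resumed NOAC treatment within 24 hours prior/after extraction compared to more than 24 hours prior/after extraction". The aim in section 3 is the relationship between last dose, "time of resuming NOAC after the procedure, and bleeding events". Section 10.4.9 says predefined subgroup analyses will be tested, without adjustment.

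Other sections fix the timing:

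- Early bleeding (4.2) is "any oral bleeding occurring after the extraction up to and including day 1 after the extraction", so the count starts at the extraction.
- Restart is instructed for the following day (7.1.2, 7.3.2).
- Date and time of bleeding are on both call forms (7.3.3, 7.3.4).
- Date and time of restart are listed only on the day 2 form (7.3.3). That call may be made on the Friday when day 2 is a Saturday, which is day 1. The day 7 form asks only whether there was an unplanned interruption, yes or no.

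No section restricts the comparison to bleeds after restart, sets a landmark, or treats restart as time-dependent.

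**The concern.** Restart time is observed after the extraction, and a bleed may influence it. A patient who bleeds a few hours after extraction and therefore waits longer joins the late group, bringing along a bleed that late restart cannot have caused. The early group loses that bleeder. This happens within each arm, so stratifying by arm does not help. The stopping half of the comparison is not affected, because the last dose precedes any bleed counted.

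The direction matters. Section 2.1 proposes that "The combination of peak plasma levels of the NOAC with an immature coagulum at the extraction site could trigger bleeding", which would make early restart look worse. The artefact makes late restart look worse, so it can hide or reverse the signal the analysis is meant to find.

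The route is plausible rather than documented. Section 2.1 says "Since bleeding events can lead to unscheduled interruption of NOAC treatment", and section 7.8 lists "Interruption of the NOAC when necessary" among the ways to treat a bleed. Both concern interruption, not a delayed first restart, and neither gives a frequency.

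**Working it through.** **The plan's own figure.** The documents give no number for this comparison. The only related figure is the sample size in 10.5 (30% versus 15%, two-sided 5%, 80% power). With unpooled variance, n = (1.960 + 0.842)² × (0.30×0.70 + 0.15×0.85) / 0.15² = 117.7, so 118 per group. It reproduces and is not affected by this point.

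**Inputs.** From 10.5: risks of 30% and 15%, mean T = 0.225, and 236 patients. Assumed, because the documents do not give them:

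- e, the share of patients bleeding before 24 h: 3, 5 or 10%
- d, the share of bleeds that defer a restart otherwise due by 24 h: 0 to 50%
- b, the share restarting late anyway: 40%

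True effect of restart timing: none, unless stated.

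**Closed form.** With L = (T − e)/(1 − e):

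- Late-group risk = [e(b + (1−b)d) + (1−e)bL] / [e(b + (1−b)d) + (1−e)b]
- Early-group risk = [e(1−b)(1−d) + (1−e)(1−b)L] / [e(1−b)(1−d) + (1−e)(1−b)]

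Example, e = 0.05, d = 0.50: L = 0.175/0.95 = 0.184. Late = (0.035 + 0.070)/(0.035 + 0.380) = 25.3%. Early = (0.015 + 0.105)/(0.015 + 0.570) = 20.5%. Gap 4.8 points.

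Late minus early, in points:

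| e | d=0 | 5% | 10% | 25% | 50% |
|---|---|---|---|---|---|
| 3% | 0 | 0.29 | 0.58 | 1.45 | 2.89 |
| 5% | 0 | 0.48 | 0.97 | 2.41 | 4.79 |
| 10% | 0 | 0.97 | 1.93 | 4.79 | 9.49 |

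This overstates the gap, because any bleed in the first 24 h may defer restart, even one that came after restart.

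**Simulation with event order.** 10,000 trials per setting, 118 per arm. Early risk is scaled by arm, with constant hazard within 0–24 h and within 24–168 h. Planned restart is uniform over 14–24 h (60%) or 24–36 h (40%). Only a bleed before planned restart can defer it, by 24 h, with probability d. Monte Carlo error is about 0.1 point.

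| Setting | d=0 | 10% | 25% | 50% |
|---|---|---|---|---|
| No effect, e=3% | 0.1 | 0.5 | 1.1 | 2.2 |
| No effect, e=5% | −0.1 | 0.8 | 1.8 | 3.6 |
| No effect, e=10% | 0.1 | 1.4 | 3.7 | 7.4 |
| Hazard doubled after restart, e=3% | −0.9 | −0.6 | 0.0 | 0.8 |
| Hazard doubled after restart, e=5% | −1.1 | −0.6 | +0.3 | +1.8 |
| Hazard doubled after restart, e=10% | −1.8 | −0.6 | +1.4 | +4.3 |

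In the doubled-hazard rows the overall risks exceed 30% and 15%.

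At e = 5% with no effect, the arm-stratified Mantel-Haenszel test rejects in 5.0, 5.3, 6.3 and 10.7% of trials.

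**Alternatives, e = 5%, same deferral rates.** Arm-stratified Cox model with restart time-dependent: median hazard ratio 1.0 under no effect (rejection 4.8–4.9%) and 2.0 under doubling. The 24-hour landmark gap under doubling stays between −0.4 and −0.6 points. Neither drifts with deferral.

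**Sensitivity to the assumptions.** Now let p be the arm's risk, f the share of bleeders who bleed before restart and within 24 h (20–40%), and b either 20% or 50%. With s = (1−b)·p·f·d, late risk is (bp + s)/(b + s) and early risk is ((1−b)p − s)/(1 − b − s).

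- Lowest (p = 0.15, b = 0.5, f = 0.2, d = 0.25): s = 0.00375; 15.6% versus 14.4%, gap 1.3 points before rounding the risks.
- Highest (p = 0.30, b = 0.2, f = 0.4, d = 0.75): s = 0.072; 48.5% versus 23.1%, gap 25.5 points before rounding the risks.

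The direction is fixed; the size depends on what is assumed.

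**The case against.** The case against is substantial.

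- Inclusion of pre-restart bleeds is inferred from silence, and deferral is not documented. Patients are told to restart the next day. A minor bleed is "any oral bleeding experienced by the patient that does not require medical contact", so usually no clinician would be advising delay. The pilot in 2.1 found its excess in delayed rather than early bleeding, which suggests a low early-bleed rate.
- Section 4.2.3 offers the 24-hour split only as an example.
- The shift is small against noise. With 22.5% risk and a 60/40 split of 236, the standard error is √[0.225×0.775×(1/141.6 + 1/94.4)] = 5.5 points, so the interval is about ±11 points.
- Even with a doubled hazard and no deferral the contrast is only −1.1 points, because the groups differ in exposure for hours out of seven days. The landmark shows no more.
- The alternative was tested with exact onset times and the correct model. Real times are recalled by telephone, and blood on a pillow has no clear onset.

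Most of this stands as a limit on weight and precision. It does not remove the point. Section 10.4.8 states the split outright, and no section orders the events. A confidence interval conveys noise but not a bias, and this bias runs against the hypothesis of interest. Clock time of the extraction and dosing regimen also affect who is late; the proposed analysis does not fully resolve that.

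**Conclusion.** The concern holds, as a minor point. As written, the comparison credits to late restart any bleed that itself caused the lateness. With no deferral there is no bias. With 5% early bleeding and 40% late restart by plan, the ordered simulation gives 0.8 to 3.6 points against late restart at 10–50% deferral. A truly doubled hazard after restart is reversed in sign from 25% deferral upward. The early-bleed rate, deferral share, late share and restart-time distribution are all assumed, and other choices give gaps from 1.3 to 25.5 points. The sample size and the primary randomised comparison are unaffected.

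**What to change.** Replace the restart bullet in 10.4.8, and align 4.2.3, with wording such as:

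> Time to first oral bleeding up to day 7, on a time-since-extraction scale, will be analysed with NOAC restart as a time-dependent exposure, stratified by treatment group, so that each bleed is attributed to restart status at its onset. As a supporting analysis, among patients free of oral bleeding at 24 h, later bleeding will be compared by restart status at 24 h, and bleeds in the first 24 h will be tabulated by whether they began before or after restart.

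Add restart date and time to the day 7 form for patients not yet restarted at the first call. A patient known not to have restarted at a call made after 24 h can already be classed as late, but the time-dependent analysis needs the actual time. Adjustment for NOAC regimen is optional. None of this implies a rule on when to restart.

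The cost is a little more analysis and one conditional field; bleed times are already collected. The price is low precision. Only about 8 to 13 bleeds occur while some patients have restarted and others have not (simulation, 5% early bleeding). With a true hazard ratio of 2, the 10th–90th percentile of the estimate is about 0.8 to 6.2 and power is about 15%. Report an estimate with its confidence interval, not a test result.

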#### 10.4.9 MULTIPLE COMPARISON/MULTIPLICITY

A limited number of predefined subgroup analyses will be tested. No adjustment to the significance level will be made.

#### 10.4.10 TABULATION OF INDIVIDUAL RESPONSE DATA

Individual data will be collected and stored.

#### 10.4.11 EXPLORATORY ANALYSES

Defined under subgroup analysis.

#### 10.5 SAMPLE SIZE

- Based on the previously cited pilot study, we estimate the rate of the primary outcome at 30% in the placebo group (7).
- We estimate to show an absolute risk reduction (ARR) of 15% This means an incidence of 15% in the tranexamic acid group.
- Confidence level is set to 95%, power is set to 80%.
- Under the above assumptions, in order to have 80% to detect a statistically significant risk difference between treatments, 118 patients per group or 236 patients in total will be required.

#### 10.6 MEASURES TO MINIMIZE BIAS

#### 10.6.1ENROLLMENT/ RANDOMIZATION/ MASKING PROCEDURES

A computer-generated block-randomization list will be generated by an independent person for treatment allocation. Labeling of the study drug and matched placebo will occur by an independent person. Sealed envelopes will contain patient number and randomization group.

#### 10.6.2 EVALUATION OF SUCCESS OF BLINDING

Not applicable.

#### 10.6.3 BREAKING THE STUDY BLIND/PARTICIPANT CODE

EXTRACT-NOAC Version 1.1
Protocol 5 July 2017

All patients can be continued to be treated based on standard-of-care irrespective of the study allocation.

#### 11 SOURCE DOCUMENTS AND ACCESS TO SOURCE DATA/DOCUMENTS

Each participating site will maintain appropriate medical and research records for this trial, in compliance with ICH E6 and regulatory and institutional requirements for the protection of confidentiality of participants

#### 12 QUALITY ASSURANCE AND QUALITY CONTROL

Following written SOPs, the investigators and study coordinators will verify that the clinical trial is conducted and data are generated, documented (recorded), and reported in compliance with the protocol, GCP.

#### 13 ETHICS/PROTECTION OF HUMAN SUBJECTS

#### 13.1 ETHICAL STANDARD

The investigator will ensure that this study is conducted in full conformity with the Declaration of Helsinki and GCP.

#### 13.2 INSTITUTIONAL REVIEW BOARD

The protocol, informed consent form, recruitment materials, and all participant materials will be submitted to the IRB for review and approval. Approval of both the protocol and the consent form must be obtained before any participant is enrolled. Any amendment to the protocol will require review and approval by the IRB before the changes are implemented to the study. All changes to the consent form will be IRB approved; a determination will be made regarding whether previously consented participants need to be re-consented.

#### 13.3 INFORMED CONSENT PROCESS

# 13.3.1 CONSENT/ASSENT AND OTHER INFORMATIONAL DOCUMENTS PROVIDED TO PARTICIPANTS

Consent forms describing in detail the study agent, study procedures, and risks are given to the participant and written documentation of informed consent is required prior to starting intervention/administering study product.

#### 13.3.2 CONSENT PROCEDURES AND DOCUMENTATION

Informed consent is a process that is initiated prior to the individual's agreeing to participate in the study and continues throughout the individual's study participation. Extensive discussion of risks and possible benefits of participation will be provided to the participants and their families. Consent forms will be IRB-approved and the participant will be asked to read and review the document. The investigator will explain the research study to the participant and answer any questions that may arise. All participants will receive a verbal explanation in terms suited to their comprehension of the purposes, procedures, and potential risks of the study and of their rights as research participants. Participants will have the opportunity to carefully review the written consent form and ask questions prior to signing. The participants should have the opportunity to discuss the study with their surrogates or think about it prior to agreeing to participate. The participant will sign the informed consent document prior to any procedures being done specifically for the study. The participants may withdraw consent at any time throughout the course of the trial. A copy of the informed consent document will be given to the participants for their records. The rights and welfare of the participants will be protected by emphasizing to them that the quality of their medical care will not be adversely affected if they decline to participate in this study

#### 13.4 PARTICIPANT AND DATA CONFIDENTIALITY

Participant confidentiality is strictly held in trust by the participating investigators, their staff, and the sponsor(s) and their agents. Therefore, the study protocol, documentation, data, and all other information generated will be held in strict confidence. No information concerning the study or the data will be released to any unauthorized third party without prior written approval of the principal investigator.

Participant details and research data, for follow-up, statistical analysis and scientific reporting, will be transmitted to and stored at the University Hospitals Leuven. Participant details and anonymized research data will be stored separately, the latter by using a unique study identification number. The study data entry and study management systems used by clinical sites and by the University Hospitals Leuven research staff will be secured. At the end of the study, all study databases will be archived at the University Hospitals Leuven.

#### 13.4.1 RESEARCH USE OF STORED HUMAN SAMPLES, SPECIMENS OR DATA

Data collected under this protocol may be used for future patient-level meta-analyses, retrospective studies or other additional studies, eg. risk factor identification, after approval by the principal investigator.

#### 14 DATA HANDLING AND RECORD KEEPING

#### 14.1 DATA COLLECTION AND MANAGEMENT RESPONSIBILITIES

Data collection is the responsibility of the clinical trial staff at the site under the supervision of the site PI. The investigator is responsible for ensuring the accuracy, completeness, legibility, and timeliness of the data reported. All source documents should be completed in a neat, legible manner to ensure accurate interpretation of data.

Copies of the CRF will be provided for use as source documents and maintained for recording data for each participant enrolled in the study. Data reported in the eCRF derived from source documents should be consistent with the source documents or the discrepancies should be explained and captured in a progress note and maintained in the participant's official electronic study record.

Clinical data (patient and procedure characteristics) and safety and efficacy outcome will be anonymized and entered into a clinical database. The data system includes password protection and internal quality checks, such as automatic range checks, to identify data that appear inconsistent, incomplete, or inaccurate. Clinical data will be entered directly from the source documents.

#### 14.2 STUDY RECORDS RETENTION

Study documents will be retained according to local institution guidelines and GCP.

#### 14.3 PROTOCOL DEVIATIONS

Protocol deviation is any noncompliance with the clinical trial protocol, GCP, or MOP requirements. The noncompliance may be either on the part of the participant, the investigator, or the study site staff. As a result of deviations, corrective actions are to be developed by the site and implemented promptly.

It is the responsibility of the site to use continuous vigilance to identify and report deviations. All deviations must be addressed in study source documents, or reported to the IRB.

#### 14.4 PUBLICATION AND DATA SHARING POLICY

Publication of the data is the responsibility of the principal investigator. The results of the study will be submitted to a peer-reviewed journal for publication.

The International Committee of Medical Journal Editors (ICMJE) member journals have adopted a clinical trials registration policy as a condition for publication. The ICMJE defines a clinical trial as any research project that prospectively assigns human subjects to intervention or concurrent comparison or control groups to study the cause-and-effect relationship between a medical intervention and a health outcome. Medical interventions include drugs, surgical procedures, devices, behavioral treatments, process-of-care changes, and the like. Health outcomes include any biomedical or health-related measures obtained in patients or participants, including pharmacokinetic measures and adverse events. The ICMJE policy, and the Section 801 of the Food and Drug Administration Amendments Act of 2007, requires that all clinical trials be registered in a public trials registry such as ClinicalTrials.gov, which is sponsored by the National Library of Medicine. The ICMJE does not review specific studies to determine whether registration is necessary; instead, the committee recommends that researchers who have questions about the need to register err on the side of registration or consult the editorial office of the journal in which they wish to publish.

